
Adverse Drug Reaction (ADR)
 
In the pre-approval clinical experience with a new medicinal product or its new usages, particularly as the therapeutic dose(s) may not be established: all noxious and unintended responses to a medicinal product related to any dose should be considered adverse drug reactions. The phrase "responses to a medicinal product" means that a causal relationship between a medicinal product and an adverse event is at least a reasonable possibility, i.e., the relationship cannot be ruled out.

Unexpected Adverse Drug Reaction
 
An adverse reaction, the nature or severity of which is not consistent with the applicable product information (e.g., Investigator's Brochure for an unapproved investigational medicinal product).

Events Meeting the AE Definition

• A new illness• The worsening of a concomitant illness• Any abnormal laboratory test results (hematology, clinical chemistry, or urinalysis) or other safety assessments (e.g., ECG, radiological scans, vital signs measurements), including those that worsen from baseline, considered clinically significant in the medical and scientific judgment of the investigator (i.e., not related to progression of underlying disease).• Exacerbation of a chronic or intermittent pre-existing condition including either an increase in frequency and/or intensity of the condition.• New conditions detected or diagnosed after study intervention administration even though it may have been present before the start of the study.• Signs, symptoms, or the clinical sequelae of a suspected drug-drug interaction.• Signs, symptoms, or the clinical sequelae of a suspected overdose of either study intervention or a concomitant medication. Overdose per se will not be reported as an AE/SAE unless it is an intentional overdose taken with possible suicidal/self-harming intent. Such overdoses should be reported regardless of sequelae.
Events NOT Meeting the AE Definition

- Any clinically significant abnormal laboratory findings or other abnormal safety assessments which are associated with the underlying disease.
- The disease/disorder being studied or expected progression, signs, or symptoms of the disease/disorder being studied, unless more severe than expected for the participant's condition.
- Medical or surgical procedure (e.g., endoscopy, appendectomy): the condition that leads to the procedure is the AE.

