2 STUDY OVERVIEW

2.1 Study Objectives

2.1.1 *Primary Objective*

The primary objective is to determine the safety of RNS60 in adult subjects (aged 18 years or older) with large vessel occlusion (LVO) and acute ischemic stroke (AIS) based on serious adverse events (SAEs) and 90-day mortality. To be eligible for this trial, subjects must have sudden onset of focal neurological symptoms within 24 hours prior to randomization consistent with an ischemic stroke. Symptoms must be persistent and present at the time of enrollment.

2.1.2 *Secondary Objectives*

The secondary objectives are to evaluate the efficacy of RNS60 in the following outcomes:

1. Reducing global disability (as measured using the Modified Rankin Scale [mRS] at 90 days)
2. Decrease in infarct volume (as defined by imaging at 48 hours)
3. Improving neurological outcome (as measured using the National Institutes of Health Stroke Scale [NIHSS] at 24 hours)
4. Reducing worsening of stroke, defined as progression, or hemorrhagic transformation, of the index stroke as documented by medical imaging that results in:
 - (a) a life-threatening situation requiring intervention, and/or
 - (b) increased disability as determined by a ≥ 4 -point increase from lowest NIHSS pre decline, and/or
 - (c) death by 48 hours or during hospital admission.
5. Reducing functional dependence (as defined by mean Barthel Index (BI) at Day 90)
6. Improving health-related quality of life, as measured by the EuroQol health-related quality of life (EQ-5D-5L) at Day 90

These outcomes will be assessed in the following hierarchical order (to control for the overall Type I error rate): first between high-dose RNS60 (1.0 mL/kg/h RNS60) compared to placebo, then both low and high dose RNS60 combined compared to placebo, and then between low-dose RNS60 (0.5 mL/kg/h RNS60) compared to placebo. In the analyses of efficacy, the combined-dose inference will be done within the statistical models by averaging the results in the two active doses and comparing to placebo. (This is in contrast to performing a separate

analysis in which subjects on active dose are treated as a single treatment arm.) The exception to this approach is the non-parametric analysis in Section 3.4.4.1, where the data in the two active arms are combined into a single group to be compared to placebo.

2.1.3 *Attributes of the Estimands*

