The attributes of the main estimand (target of estimation), used for the primary analysis of the highest ranked efficacy endpoint (modified Rankin Scale (mRS) score) are defined below. Although the primary objective of this study is related to safety, analysis of the efficacy endpoints (secondary objectives of the study) will be based on a pre-defined hierarchy and therefore, an estimand is defined.

- The **population** is defined as the intent-to-treat study population (see Section 3.2.3).
- The corresponding **variable** to be obtained for each subject required to address the scientific question is disability based on the mRS score at Day 90. The mRS will be evaluated as a binary outcome (0-2, 3-6).
- The **population level summary** considered in this study is the odds ratio between RNS60 1.0 mL/kg/h and placebo 1.0 mL/kg/h.
- The **treatments** to be compared are RNS60 1.0 mL/kg/h and placebo 1.0 mL/kg/h. The treatments will be compared according to the randomized groups, regardless of the treatment that was actually received. In accordance with the treatment policy principle, all available data will be used in the analysis, regardless of e.g., premature discontinuation of study medication or administration of any concomitant treatment.
- The **intercurrent events** (ICEs) considered as potentially impacting results and/or interpretation are:
 - Premature discontinuation of study treatment
 - Death
 - Coronavirus Disease 2019 (COVID-19) pandemic related events (assessments that were missed due to COVID-19).

For the data that are missing due to premature discontinuation of study treatment, an assumption of Missing At Random (MAR) will be made. Sensitivity analyses will be conducted using an assumption of Missing Not At Random (MNAR). No specific imputation will be done for these missing data, because the likelihood-based analysis approach can manage subjects with incomplete data under the assumption of MAR.

For the data that are missing due to COVID-19, an assumption of MAR will be made for all analyses, both primary and sensitivity analyses.

For the mRS, NIHSS and BI endpoints death is included as part of the scoring, so no imputation of these endpoints is required for subjects who die. Similarly, for the worsening of stroke endpoint, death represents a worsening. For the infarct progression end point, death will be represented by a missing value.

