Worsening of stroke is defined as progression, or hemorrhagic transformation of the index stroke, as documented by brain imaging, which is (a) life-threatening requiring intervention and/or (b) results in increased disability as gauged by a ≥ 4-point increase from lowest National Institutes of Health Stroke Scale (NIHSS) pre decline and/or (c) results in death.

5) Barthel Index at Day 90.

The BI is an index of functional independence. Its values range from 0 to 100, with higher scores indicating greater independence.

Table 4. Scales and score range in BI

| Item | Score range |
|-----------------------------------|-------------|
| Feeding | 0-10 |
| Bathing | 0-5 |
| Grooming | 0-5 |
| Dressing | 0-10 |
| Bowels | 0-10 |
| Bladder | 0-10 |
| Toilet use | 0-10 |
| Transfers (bed to chair and back) | 0-15 |
| Mobility (on level surfaces) | 0-15 |
| Stairs | 0-10 |

Item scores vary in increments of 5 points.

6) Health-related quality of life, as measured by the EuroQol health-related quality of life (EQ-5D-5L) at Day 90.

EQ-5D-5L is developed by EuroQol Research Foundation and is a generic instrument for measuring and describing health-related quality of life.

It consists of two elements, a 5-item questionnaire and an EQ-Visual Analogue Scale (VAS). Both elements are interviewer administered by study staff.

EQ-5D-5L is a version that further improves the sensitivity of EQ-5D-3L, provides respondents with a wider range of options to describe their health and is comprised of five response levels to five different dimensions.

- **5-Item Questionnaire:** The questionnaire provides a simple descriptive profile of health state. The questionnaire comprises 5 dimensions (mobility, self-care, usual activities, pain/discomfort, anxiety/depression) and each dimension has 5 response levels (1-no problems, 2-slight problems, 3-moderate problems, 4-severe problems,

5-unable to/extreme problems). The resulting 5-digit code corresponds to the response of each dimension of the health state. For instance, 11111 and 55555 indicate the best health condition and the worst health condition, respectively.

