3.1.7 Handling of Death

Subjects who die during the study will be scored as follows for all scheduled visits following the death: 6 for mRS, 42 for NIHSS and 0 for BI. The value 6 for mRS is part of the mRS definition. The values for NIHSS and BI are conventions, consistent with the worst possible score.

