Additionally, neurological functioning at Day 90 will be examined by NIHSS scores at Day 90 between the three treatments (RNS60 1.0 mL/kg/h, RNS60 0.5 mL/kg/h, and placebo 1.0 mL/kg/h). GLM analysis and missing data imputation analysis at Day 90 will be performed using the same approach described above for neurological functioning using 24-hour NIHSS scores.

4. The proportion of subjects with worsening of stroke over the 48-hours/duration of admission:

Worsening of stroke is defined (i.e., Yes or No) as: progression, or hemorrhagic transformation, of the index stroke as documented by medical imaging and that is (a) life-threatening requiring intervention and/or (b) results in increased disability as gauged by a \geq 4-point increase from lowest NIHSS pre decline and/or (c) results in death. Subjects with worsening of stroke will be identified based on a \geq 4-point increase in their worst minus best NIHSS score and adverse events status (life threatening requiring intervention or death) as collected in the CRFs.

The simple effect of treatment on worsening stroke at 48 hours/admission duration will be examined by comparing the proportion of subjects who had worsening stroke (Yes or No) between the three treatments (RNS60 1.0 mL/kg/h, RNS60 0.5 mL/kg/h, and placebo 1.0 mL/kg/h) using GLM using residual pseudo-likelihood with a subject-specific expansion (RSPL) assuming a binary distribution. Covariates include the Age, baseline NIHSS, and baseline ASPECTS as binary factors used for block urn randomization, log of baseline infarct volume, baseline perfusion status, baseline occlusion location, and study site.

The predicted probability for each treatment group and LS mean difference between high-dose and placebo and low-dose and placebo groups along with the 95% CIs will be provided using the LSMEANS/DIFF statement. The comparison of the two combined active arms versus placebo will be performed using the LSMESTIMATE statement with the ILINK option. The odds ratio will also be calculated. The P-value for the hypothesis testing will also be provided. Treatment difference will be assessed with a 2-sided alpha level of 0.05.

The sample SAS code planned for the analysis is outlined below.

5. Barthel Index.

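### The rule that identifies worsening of stroke (ranks 4, 9 and 14) drops the imaging and cause conditions in the endpoint's own definition, so in-window deaths from other causes count as worsening

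*SAP*

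**What the plan says.** **Definition.** SAP 2.1.2, objective 4, requires "progression, or hemorrhagic transformation, of the index stroke as documented by medical imaging that results in" one of three outcomes: (a) a life-threatening situation needing intervention, (b) an NIHSS rise of at least 4 points from the lowest score before the decline, or (c) "death by 48 hours or during hospital admission". SAP 2.3.2(4) keeps the same condition, "as documented by brain imaging, which is (a) life-threatening requiring intervention", and continues with limbs (b) and (c). SAP 3.4.2(4) repeats the definition, as do Protocol 3.1.2 and 8.1.9. In each, the imaging-documented event comes first and the death must result from it.

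**Handling of death.** SAP 2.1.3 says: "Similarly, for the worsening of stroke endpoint, death represents a worsening". SAP 3.1.7 adds: "Subjects who die during the study will be scored as follows for all scheduled visits following the death: 6 for mRS, 42 for NIHSS".

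**Identification of cases.** Directly after restating the definition, SAP 3.4.2(4) finds cases from a difference of at least 4 points in "worst minus best NIHSS score and adverse events status (life threatening requiring intervention or death) as collected in the CRFs".

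**Adverse event collection.** Protocol 10.3 (Appendix 4) lists among events that are not AEs: "The disease/disorder being studied or expected progression, signs, or symptoms of the disease/disorder being studied, unless more severe than expected" for that participant.

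**Window.** SAP 2.1.2 and 3.4.2(4) use 48 hours or the hospital admission. SAP 2.3.2(4), Protocol 3.2.2 and Protocol 9.3.3 use 90 days.

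**The concern.** The definition and the derivation describe different endpoints. A fatal pneumonia or cardiac death inside the window, with no progression on imaging, fails the definition but is an event under SAP 2.1.3 and under the adverse event limb of 3.4.2(4). Two programmers working from the same SAP could derive different binary outcomes.

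The endpoint holds ranks 4, 9 and 14 in a hierarchy meant to control Type I error. Mortality is already a primary safety endpoint, and death already takes the worst value on mRS, NIHSS and Barthel Index. Worsening of stroke is the item that should add stroke-specific information, and unrelated deaths weaken it. SAP 6.4 reports no significant change from the protocol beyond specifying analyses and further defining endpoints, and the SAP governs where the two differ. A reader would therefore not know that the case definition had moved.

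A smaller issue concerns non-fatal limb (a) events. They are sought in AE records, and whether a progression is recorded there depends on the investigator's view of what was expected. Capture may differ between sites.

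**Working it through.** The plan gives no event rate, effect size or power for this endpoint, so there is no stated figure to reproduce. The main check is textual, and the arithmetic only illustrates direction and scale.

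**1. Conditions side by side**

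| Source | Imaging-documented progression or transformation? | Must the death result from it? |
|---|---|---|
| Definition: SAP 2.1.2, 2.3.2(4), 3.4.2(4) | Yes | Yes |
| Death rule: SAP 2.1.3 | Not mentioned | Not mentioned |
| Identification rule: SAP 3.4.2(4), second sentence | Not mentioned | Not mentioned |

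The identification sentence joins its two data sources with the word *and*. I read this as a list of sources, because the definition's limbs are and/or. On a strict both-required reading the rule departs from the definition in another way, and SAP 2.1.3 still counts the death.

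**2. The imputed NIHSS.** If the 42 from SAP 3.1.7 enters worst minus best, the limb is met when 42 − best ≥ 4, that is, for any best score of 38 or less. A death followed by a scheduled in-window visit would then nearly always meet the NIHSS limb as well, whatever its cause. The SAP does not say that the 42 enters this calculation, and does not rule it out.

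**3. What the documents give on size.** Target 100 participants at 1:1:1, so 100/3 ≈ 33 per arm. The only death figure is the 10% attrition from stroke death in SAP 2.2.4, about 10 in total or 3.3 per arm. No rate is given for deaths from other causes or for worsening.

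**4. Illustration (rates assumed).** Let p be the true rate of definition-meeting events and q the probability of an in-window death without documented progression, equal in both arms.

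Observed rate = p + q(1 − p).

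Placebo p = 0.20, active p = 0.10:

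- q = 0: OR = (0.10/0.90)/(0.20/0.80) = 0.44.
- q = 0.03: placebo 0.20 + 0.03 × 0.80 = 0.224; active 0.10 + 0.03 × 0.90 = 0.127; OR = (0.127/0.873)/(0.224/0.776) = 0.50. Share of placebo events outside the definition: 0.024/0.224 = 11%.
- q = 0.10: placebo 0.28; active 0.19; OR = (0.19/0.81)/(0.28/0.72) = 0.60. Share: 0.08/0.28 = 29%.

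| Assumed true rates (placebo, active) | OR at q = 0 | OR at q = 3% | OR at q = 10% | Placebo share outside definition (q = 3%, 10%) |
|---|---|---|---|---|
| 10%, 5% | 0.47 | 0.59 | 0.72 | 21%, 47% |
| 20%, 10% | 0.44 | 0.50 | 0.60 | 11%, 29% |
| 30%, 15% | 0.41 | 0.45 | 0.52 | 6%, 19% |

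Power with 33 per arm, two-sided 0.05, by the unadjusted normal approximation for two proportions (not the planned mixed model): at 20% and 10% it is 20% for q = 0, 18% for q = 3% and 14% for q = 10%.

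**5. Missed events.** If 25% of true events are missed in both arms and q = 0, the rates become 0.15 and 0.075. The OR is 0.46 against 0.44, and power is 16% against 20%. Uniform under-capture costs events but barely moves the estimate. Under-capture that differs by site or arm cannot be sized from the documents.

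**The case against.** **It is only loose wording.** SAP 3.4.2(4) gives the full definition just before naming its data sources, so the second sentence may only say where to look. That is a fair reading, and it makes this an internal conflict rather than an outright replacement. It does not explain SAP 2.1.3, which is unconditional.

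**Death as failure is a legitimate composite strategy.** It is. SAP 2.1.3 lists death as an intercurrent event and treats it alongside the worst scores on the other scales. But a composite should be declared, and every statement of this endpoint's definition says something narrower. The strict rule also has a cost, which the objection rightly raises: a patient who dies without documented progression becomes a non-event, which looks favourable. The supportive analysis below addresses that.

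**Stronger readings that the documents do not support.**

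- A reader might infer that sites are told to keep life-threatening progression out of the AE records. The Protocol 10.3 exclusion covers only expected progression and excepts anything more severe than expected. Hemorrhagic transformation is not named in it. Protocol 8.2.2 asks about unexpected worsening, all deaths to Day 90 are reported as SAEs, and the NIHSS limb is a backstop for non-fatal cases. What remains is dependence on individual judgment.
- A reader might infer that every death in the trial is counted. Under the 48-hour or admission window, deaths after discharge are outside the endpoint. Only the 90-day statements would bring them in.
- A reader might infer that the imputed 42 certainly enters the NIHSS limb. SAP 3.4.2(4) refers to data collected in the CRFs, and an imputed score can be read as not collected.
- A reader might quote a firm percentage of misclassified events. Any such figure rests on assumed rates.

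**Conclusion.** The mismatch stands on the text. As written, in-window deaths from causes other than imaging-documented progression or transformation are classified as worsening of stroke, contrary to the endpoint's own definition, and the SAP does not declare this as a change. With equal non-stroke death rates across arms the effect is dilution toward no difference; no inflation of false positives has been shown. The figures above depend on assumed true rates, assumed q and equality of q across arms, and they show direction only. The number of deaths involved also turns on the unresolved window.

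Inconsistent capture of limb (a) events is possible but secondary, and cannot be sized.

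This is a should-fix. The endpoint is secondary in a trial with no power calculation, and rank 4 is confirmatory only if ranks 1 to 3 succeed. The choice must still be made before unblinding, since a later choice could be driven by the data.

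**What to change.** Amend the SAP before unblinding:

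1. In 2.1.3 and 3.4.2(4), make the ranked endpoint require imaging-documented progression or hemorrhagic transformation of the index stroke plus (a), (b) or (c). Measure the NIHSS rise from the lowest preceding score, as the definition does; worst minus best by itself has no time order, so a fall from 16 to 8 would also give 8 points. Protocol 10.2.2 already sends all brain imaging up to the Day 90 MR to the core lab.
2. State that the NIHSS of 42 assigned after death in 3.1.7 is not used in the NIHSS limb of this endpoint.
3. Pre-specify worsening of stroke or death from any cause as a supportive analysis, so that deaths without documented progression do not appear only as non-events.
4. Use one analysis window, reconciling 2.1.2 and 3.4.2(4) with 2.3.2(4) and the protocol, and record the decision in 6.4.

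Do not change the AE reporting rules for this purpose. Recording every qualifying progression as an AE would turn serious cases into SAEs and so alter the primary safety endpoint, and it would need a protocol amendment.

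**Cost.** A few sentences of SAP text, revised derivation programming and one extra table. The core lab's listed tasks do not expressly include calling progression or transformation for this endpoint, so an added read may be needed unless the Imaging Charter, which is not among the documents, already covers it. The ranked test will have fewer events, and a death before any follow-up scan will not count in it.

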2.2 Study Design

2.2.1 Overview

This trial is a Phase 2, block urn randomized, blinded assessor, placebo-controlled, parallel group, two-dose (high and low), and longitudinal (pre-stroke, post-treatment, 48-hour, discharge, and Days 30 and 90) study with equal arm sample sizes (1:1:1). All participants in the trial will be followed for 90 days (or until death if prior to 90 days). Participants are considered to have completed the study if they have remained in the study until Day 90 or they have died prior to Day 90. The end of the trial is defined as the date the last enrolled participant has completed their Day 90 visit/contact.

The trial's primary aim is to demonstrate the safety of RNS60. As a secondary aim, the study will provide first data on whether RNS60 may reduce global disability, improve neurological outcome, reduce worsening of stroke and reduce infarction volumes. Superiority of the higher dose is hypothesized over placebo and of the lower dose over placebo is hypothesized for all secondary and tertiary objectives.

AIS large vessel occlusion participants who are selected for Endovascular Thrombectomy (EVT) will be given a 48-h infusion of either 0.5 mL/kg/h RNS60 (up to a maximum of 65 mL/h), 1.0 mL/kg/h RNS60 (up to a maximum of 130 mL/h), or 1.0 mL/kg/h (up to a maximum of 130 mL/h) placebo (normal saline) starting within 30 minutes of randomization (but prior to arterial access closure).

Randomization will be done with block urn randomization to balance age (<80 vs. \geq 80), NIHSS score (6-10 vs. >10), and Alberta stroke program early computerized tomography score (ASPECTS) (5-7 vs. 8-10) for a total of 8 urns.

Table 1 shows the schedule of activities of randomized participants.

Table 1: Schedule of Activities for Randomized Participants

| Visit/Contact | V1 | V2 | V3 | V4 | V5 | V6/ End of Trial |
|---|---------------------|-------------------|--------------------------------|------------------------------------|---------------------|---------------------|
| Day | Day 0 Baseline | Day 1 Post-EVT | Day 2/or early discharge | Day 6 ¹ or discharge | Day 30 ² | Day 90 ² |
| Window | (24 h+/-4h) | | (48 h+4h) | (-5 d) | | (-21 to +7d) |
| Informed consent | X | | | | | |
| Regained capacity informed consent ³ | | | X | X | X | X |
| History and physical examination ⁴ | X | X | X | | | |
| Weight ⁵ | X | | X | | | |
| Vital Signs (BP, HR, Temperature) ⁶ | X | X | X | | | |
| Chest radiograph | X ¹² | X | X | | | |
| Electrocardiogram ⁷ | X ¹² | X | X | | | |
| Randomization/ Study drug administration | X | X | X | | | |
| Continuous telemetry ⁷ | X | X | X | | | |
| Mortality | | X | X | X | X | X |
| NIHSS ¹³ | X | X | X | X | X | X |
| mRS | X | | | X | X | X |
| Barthel Index | X | | | | X | X |
| EQ-5D-5L | | | | | | X |
| Imaging (NCCT & mCTA) | X | | | | | |
| Endovascular Procedure | X | | | | | |
| MRI head ⁸ | | X | X | | | X |
| Laboratory Assessments | X ⁹ | | X | | | |
| Pregnancy test ¹⁰ | X | | | | | |
| Blood collection for RNA analysis ¹¹ | | X | X | | | X |
| Blood collection for Plasma Biomarker | | X | X | | | X |
| AE | Collected to Day 90 | | | | | |
| SAE | Collected to Day 90 | | | | | |
| Prior medications | X | | | | | |
| Concomitant medications | | | | Collected to Day 90 | | |

1. Visit will occur at Day 6 or hospital discharge if prior to Day 6.
2. At Day 30 and Day 90 it is preferred that participants will return to clinic. If an in-clinic visit is not possible the participant can be contacted by telemedicine (preferred) or by telephone (last option).
3. If the original process involved anyone other than the participant (and if required), site staff will make ongoing efforts until: (1) regained capacity consent is obtained from participant, (2) death, or (3) completion of the Day 90 assessment.
4. Physical exam every 8-12 hours during Day 1 and Day 2.
5. At baseline estimated or actual weight will be collected. If an estimated weight was collected at baseline, actual weight should be collected as soon as feasible and prior to discharge.
6. Vital signs (Blood Pressure (BP), Heart Rate (HR) only) will be recorded immediately before and after completion of the study drug infusion, and every 8-12 hours during Day 1 and Day 2, temperature will be collected at baseline only if standard of care.
7. Abnormal electrocardiogram or continuous telemetry result that suggests clinical instability will prompt a formal cardiology consult.
8. Magnetic Resonance Imaging (MRI) head with perfusion imaging within approximately 2h post-EVT on Day 1 and at 48h +/- 4h. MRI head only at 90d.
9. Blood should be drawn at baseline, but results are not required prior to randomization. Results from primary hospital (within 8 hours) are accepted.
10. If the participant is female and is of childbearing potential a pregnancy test (urine or serum point-of-care pregnancy test) must be collected at baseline, but result is not required prior to randomization.

11. Day 1 collection 12-24 h (+/-4 hours) after additional consent is obtained for optional collection.
12. Results from the baseline Electrocardiogram (ECG) and Chest X-ray(CXR) are not required prior to randomization.
13. NIHSS score is obtainable in-person or via telemedicine visit only (not over the phone).

D = days; h = hours

2.2.2 *Randomization and Blinding*

All subjects will be centrally assigned according to the study's Randomization and Study Product Management Plan to a randomized and blinded study intervention (i.e., RNS60 0.5 mL/kg/h, RNS60 1.0 mL/kg/h, or placebo 1.0 mL/kg/h) using block urn randomization tables (8 urns). The randomization table will be set for up to 126 subjects per urn to ensure no urn can be filled prior to enrollment completion. Each site will have its own randomization table. All subjects are identified by a 5-digit number (e.g., 01-001), consisting of a unique 2-digit site number followed by a 3-digit subject number. Each subject number is unique and will not be reused.

Treatment allocation will be assigned using 1:1:1 randomization of three arms with block urn randomization by age, NIHSS score, and ASPECTS. Randomized allocation will be fully concealed by having allocations based upon random assignment and blinded by the use of RNS60 and placebo infusion bags and labels with identical visual appearance. The lower rate of infusion associated with the low-dose RNS60 poses potential for unblinding of study staff involved with infusion administration to the low-dose group, however assessors and subjects will remain blinded. Each infusion bag will have a unique 5-digit identification number.

The purpose of using block urn randomization is to minimize the possibility of imbalance of treatment assignment by age, NIHSS score, and ASPECTS due to the small sample size. Block urn randomization provides consistent imbalance control but provides greater allocation randomness compared with permuted block design and can be used for more than three arms.

All participants, investigators, their clinical staff, local laboratories, study personnel, the data management group, and the sponsor staff and delegates will be blinded to the randomization codes and study drug assignment. All study personnel (Contract Research Organization (CRO) and Sponsor and sites) will remain blinded to this data until database lock, at minimum. In the event of emergency unblinding due to participant safety, the Investigator may request unblinding of that participant only. Processes and procedures for unblinding will be accordance with the study protocol, Data Management Plan, Safety Management Plan, and any applicable CRO or Sponsor Standard Operating Procedures.

2.2.3 *Study Drug*

RNS60 is [REDACTED]

[REDACTED] RNS60 has demonstrated exceptional safety in rodent and non-human primate toxicity studies. Additionally, RNS60 has demonstrated significant efficacy in a non-human primate model of acute ischemic stroke without any indications of adverse effects. In all clinical studies to date, RNS60 has been well tolerated. In this study, infusion will begin prior to the completion of the endovascular revascularization procedure (defined as the time of arterial access closure) and complete 48h after the infusion is initiated.

